9.4.4. Post enrolment transition from study worker home visits (protocol v16.0)

To 3 March 2022, there were 450,275 individuals are currently active in the study (still receiving home visits). Under protocol v16.0, a phased approach will be taken to offer existing active participants the option to transition from study worker home visits to posted sample kits with either online or telephone completion of the questionnaire. The phased approach enables the study to comply with the Central Digital and Data Office (CDDO) requirements (https://www.gov.uk/service-manual/service-standard; mandatory for the study to comply with given the government funding of a digital service), whilst also ensuring that procedures are tested before being rolled out to many thousands of participants and that statistical comparisons can be made between answers to questionnaires administered by study workers or online/over the telephone.

Specifically, we envisage a four stage approach, described below with approximate timings; however, these may be accelerated or delayed depending on any logistical or other issues identified. In each stage, participants will receive an email or letter (depending on their existing preference for receiving study information) informing them of the future cessation of study home visits and the arrangements for future assessments, including a step-by-step guide to the process of opting to continue in the study. This will be based on the main Participant Information Sheet for adults aged 16 years and older, excluding the information about registration and consent, and weekly visits for the first month, since all existing participants will have been in the study for at least 3 months at the time they move to the new approach to delivery. The communication will be sent between the scheduled penultimate and final home visit wherever possible, providing an additional opportunity for participants to discuss the future approach to delivery with their study worker. Some invitations may only be sent after the final scheduled home visit; however, all participants have already been informed through an approved communication about the changes to the mechanism of delivery (Substantial Amendment 16). Further, study workers will also provide participants with a short leaflet highlighting the action needed to remain in the survey at study worker visits in June and July 2022, to further increase awareness of the changes. After the initial communication inviting them to remain in the study under the new approach, participants will have the option to register their interest in continuing in the study either immediately or subsequently. There is no time limit to participants registering interest, but there would be no further communcations from the study to the participant after a second reminder 60-80 days after the initial communication (see below). Each participant would initially opt-in by telephone, but an online process to register interest in continuing the study will be provided as soon as possible. Participants would receive an initial reminder about registering for the new approach 20-40 days after the first communication (currently 30 days but may be varied depending on the response rate over time), and a final reminder 60-80 days after the initial communication (currently 70 days, but may be varied depending on the response rate over time), approximately following the times when participants would have expected to have study worker visits. In order to use mixed modes to reach participants, this second reminder would be by letter wherever possible (dependent on the total numbers not opted in by this timepoint given the fixed funding to support this) (if necessary, prioritising letters based on participant characteristics with lower opt-in rates after email invitation and email first reminder (as per original communications preference), for example older participants). After this second reminder, a previous participant will receive no further

communication about the study. Whilst limiting the period of transition would avoid large gaps in individual participant's longitudinal data, any specific time period is arbitrary. Early data from Stage 1 indicate that a continued increase in opt-in rates over time from the first week after the initial communication; as the UK moves to 'living with COVID-19' and participants return to work, school and previous activities, with a lower priority being placed on COVID-19, it is important to maximise opt-in from existing participants, even if there is a short gap in their longitudinal data, rather than having to recruit new participants with no prior longitudinal data at all in order to meet targets, and to allow existing participants who wish to move to the new approach the opportunity to do so.

Contact to register willingness to continue in the study will be understood to extend existing consent since no other procedures (self-swab, self-fingerprick by the participant, questionnaire) will change, only the mode by which these are delivered. Each participant who registers interest in continuing will be asked their preference for questionnaire completion (online or by telephone), future contact regarding study communications (e.g. notification of assessment windows) and test results (email or letter) and whether they have the ability to use a priority post box in general or will need to use a courier (as per Section 9.1.2 above, summarised in Appendix I, Figure 6). Participants will also be asked whether they would like to continue to receive compensation for study assessments (see Section 16.8), and if yes, whether they wish to receive these vouchers by email or post (separate preference to study communications). Email addresses and telephone numbers will be verified for those who telephone to opt in to ensure security of this information; participants wishing to provide an email address for the first time will be asked to call the contact centre. All participants from a household who register interest in continuing will have the same first assessment window for the new approach; this will be scheduled to continue the household's monthly visit schedule, within the existing study windows wherever possible with the aim of achieving as smooth a transition in completed test results as possible (see Figure 4 below). The start of this first assessment window will become T=0 for the new system, with assessments scheduled monthly from this point onwards. Flow and example timeline for existing participants opting in is summarised in Appendix I, Figures 16 and 17, and communications with existing participants summarised in Appendix I, Figure 18. Participants who opt to continue in the study will be emailed links or posted a guide on how to take a swab and how to take blood if consent has previously been provided for this, together with step by step guide to what will happen in the survey given their preferences (post box vs courier etc).

The required reduction in sample size and transition to the new approach to delivery from 1 April 2022 will be achieved as follows. First, all participants will be informed that from 1 April 2022, the compensation vouchers will reduce from £25 to £20 per assessment, and that, if they prefer not to continue the study, they should contact the contact centre to withdraw. The numbers choosing to withdraw are unknown, but could be 5-25%. Depending on this, up to 20% of existing participants will be contacted in April 2022 to thank them for their participation and explain that the study has a reduced sample size and it will no longer be possible to continue to include them. Priority will be given to retaining participants with under-represented characteristics, including non-White ethnicity, higher deprivation, smaller household sizes, giving blood by fingerprick and with longest participation and fewest missed visits in the study wherever possible, to improve overall representativeness and maximise the value of the most complete histories of SARS-CoV-2 infections to meet objectives.

Remaining participants will be invited to transition to the new approach to delivery in four stages. Stages 2-4 form a randomised stepped wedge design, enabling statistical comparisons to be made between

answers to questionnaires administered by study workers or online/over the telephone, and swabs/bloods returned by different mechanisms, and ensuring that the study retains sufficient numbers under plausible assumptions to continue to report on positivity (see below).

- Stage 1 (target start date for opt in invitations 21 March 2022²) is a small scale transition of up to 2,000 households, sampled purposively to capture the experience of a range of ages, ethnicities, deprivation, household size and reported long-term health conditions, in transitioning to the new approach. All participants in Stage 1 will be asked to provide feedback on their experience of the new arrangements in order to improve logistics through short surveys; a purposively selected sub-sample will be invited to qualitative interviews (see Section 9.4.4.1 below for details). CDDO term this small scale initial transition the "private beta". CDDO approval is required to proceed to Stage 2.
 - As new recruitment was temporarily paused during the transition to the new approach, once recruitment resumes under the new approach, quantitative and qualitative feedback will also be sought from new participants, particularly around their experience of enrolment and initial weekly assessment, in order to improve this.
- Stage 2 (~4 weeks, target start date for opt in invitations 18 April 2022) is a larger transition of a random 25% of participants not included in Stage 1 (and not dropped from the study, as described above) who would have had study worker visits due in each of the following 4 weeks. CDDO term this small scale initial transition the "public beta". Participants in Stage 2 will have the opportunity to provide feedback on their experience of the new arrangements through the same short surveys as Stage 1.
- Stage 3 (~4 weeks target start date for opt in invitations 16 May 2022) is a larger transition of a random 35% of participants not included in Stage 1 who would have had study worker visits due in each of the following 4 weeks.
- Stage 4 (~4 weeks target start date for opt in invitations 13 June 2022) is the final transition of the remaining 40% participants.

Assuming that 90% of participants respond to the initial communication, increasing to 99% after the 20-40 day reminder, that ultimately 81% of participants chose to transition to the new format (increasing gradually predominantly over the 6 weeks from the initial communication), that 90% respond in any given assessment window, that individual assessment window non-response is 10%, that overall 97% of sample kits posted that are returned are done so a median 7 days after the start of each assessment window, this staged approach would lead to the number of completed swab tests shown below in Figure 4 over weeks from start of Stage 2, assuming that a theoretical 100,000 participants are currently visited each week (approximately the case). If a greater percentage chose to continue in the study, then the final numbers will be higher, but the trends will be similar. As the percentages who will choose to continue are unknown, randomisation will be stratified, with households with under-represented characteristics, longest participation and fewest missed visits prioritised for randomisation in Stage 2 and 3, and other participants randomised across Stages 3 and 4. Depending on the percentage who agree to continue, some participants originally planned to be randomised to Stage 4 may need to be contacted to explain that it will no longer be possible to continue to include them, given the reduced sample size.

© Copyright: The University of Oxford and Oxford University Hospitals NHS Foundation Trust 2019 Page 52 of 113

² All dates are indicative targets, depending on approval from the Research Ethics Committee, completion of the database for online/telephone questionnaire completion, and, for later stages, approval from CDDO and absence of need to make other changes based on participant feedback.

Clinical Research Protocol Template version 15.0

During each of Stages 2, 3 and 4, adjusted estimates of swab and antibody positivity (adjusting for sex, age, ethnicity and region as used in the post-stratification (see Section 11.2), and also further adjusting for deprivation and household size) would be compared between those randomised to transition to the new approach to delivery and returning swab tests and those randomised to still receive study worker visits. This, together with analyses of response rates by these factors, will enable an assessment of whether future adjustments for response rates are necessary.

Study worker visits will continue to be scheduled under protocol v16.0 for all participants who have not yet received their invitation to continue the study under the new approach (up to one home visit will be scheduled after this invitation, but if the household does not attend, no further home visits will be scheduled). Study visits will stop as soon as these final scheduled visit dates have passed.

Monthly visits will initially be implemented as 31 days apart, but given substantial uncertainty in the percentage of testing windows that will be completed under the new approach, this schedule may be extended by up to 5 days (to 36 days) or shortened by up to 3 days (to 28 days) in order to achieve the overall sample targets with the (unknown) number of participants who choose to opt in to the new approach. This does not impact analysis as the key objectives relate to rates over calendar time, not by time since participants joined the study.

[figure not shown]

Figure 4 Illustration of the impact of staged approach to transition a theoretical 100,000 participants on the number of completed tests per week

9.4.4.1. Collection of quantitative and qualitative data for process evaluation during the transition

The goal of the quantitative and qualitative process evaluation 1 is to test how the new approach to delivery was actually used and received in practice. Process evaluation will include surveys offered to all participants invited to and opting to continue the study in Stages 1 and 2, and interviews in a sub-sample of those from Stage 1. Those newly recruited after the temporary pause in recruitment during the transition to the new approach will also be invited to similar quantitative and qualitative feedback.

Quantitative process evaluation

We will approach all participants invited to and opting to continue the study in Stages 1 and 2, and those newly recruited after the temporary pause in recruitment during the transition to the new approach, to record their experiences of the new approach to delivery. To ensure that we capture their views at each stage of the process, this will involve the option to complete ~5 short questions after opt in (online or by phone) for existing participants or enrolment for new participants, ~5 short questions after any participant opts out of the testing window and a slightly longer survey (~20 questions) after completing the questionnaire to cover the overall end-to-end process, the questionnaire itself (e.g. layout, clarity of questions, any problems with browsers if online), and the home testing/returns (e.g. getting to a postbox, booking couriers). Questions will include ease of use, understanding of the system from the communications provided, clarity of instructions and the general approach, and use Likert scales to capture strength of views. We will include free text boxes for participants to add further information about experiences regarding the transition, and explicitly elicit suggestions for improvement. Completing these questions would be understood consent to participate in this component of the process evaluation. Participants would be offered the option of completing these questions by phone if they call to opt in/opt out of a testing window or complete the questionnaire by telephone, or could be emailed a link to complete the questions online. The link to the final questions will be included at the end of the

Clinical Research Protocol Template version 15.0

© Copyright: The University of Oxford and Oxford University Hospitals NHS Foundation Trust 2019 Page 54 of 113 questionnaire for those choosing to complete the main survey questionnaire online. As this feedback would be sought only within Stages 1 and 2, and for a relatively small number of new participants (enrolled only to maintain targets), it will be recorded using a separate survey tool (Smart Survey) to the main study database. On Smart Survey, participants would be identified only by their age in years at last birthday, sex, region and household size (no personal identifiable information). Analysis will be conducted at least every 2 weeks to ensure that problems with the logistics of the transition are addressed swiftly.

Qualitative process evaluation

All interviews will be semi-structured and conducted by the Office for National Statistics either by telephone or online. Interviews will be audio recorded by the interviewers (and explicit consent will be sought for this). Participants invited and opting to continue the study in Stage 1, or newly recruited after the temporary pause in recruitment during the transition to the new approach, will be eligible for inclusion regardless of age or sex, provided they are willing and able to give informed consent for participation in the qualitative study. Consent will be collected verbally and recorded by the interviewer before any interview starts, and a copy of the consent form sent securely to each participant. Participants invited to interviews will be purposively sampled by gender, age and whether they chose to complete questionnaires online or by telephone, and return samples by post or courier; and if possible also by geography, deprivation and other under-represented characteristics until saturation of experiences/views (expect 20-30 interviews). Participants would be approached by staff from the Office for National Statistics once they have completed their first assessment under the new approach to delivery, and interviewed at a time convenient to them. The information provided to participants invited to join Stage 1, or as new participants to the survey as a whole, will include the possibility that they may be approached for interview (which is optional) and that they will be asked to provide feedback via a survey (also optional).

Interviews will last approximately 30-45 minutes and participants will receive a voucher worth £20 as compensation for their time. Semi-structured, open ended questions will be used to explore individual experiences of using the new approach to delivery.

Interviews will all be audio-recorded and fully transcribed by ONS staff. Transcription will be done using Microsoft Teams transcription software and the audio recording will be captured through a separate computer program. Once the transcriptions are sense checked, the interviewers will anonymise them, by replacing any names or personal identifiers with a participant number and pseudonym in the saved copy of the transcript which will be stored in a limited access Sharepoint folder at the Office for National Statistics. Personal data will be linked with participant numbers stored on a secure network drive at the Office for National Statistics. Pseudonyms are used so that results can be easily discussed whilst protecting participants' identities. Direct quotations used in any reports or other outputs from the study will be anonymous with all identifying details removed.

To ensure that we remain open to and grounded in participants' perspectives, we will carry out thematic analysis of all textual data. Coding frameworks will be developed by two researchers and then iteratively refined, with agreement on all final coding by two independent researchers. Themes and interpretation of findings will be discussed with the wider team, to ensure consistency, particularly comparing and contrasting themes identified from the different approaches to delivery.

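### The stepped-wedge mode comparison omits factors that decide stage (length of participation, missed visits, randomisation stratum), leaving it open to confounding by prior adherence

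*Protocol*

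**What the plan says.** Protocol Section 9.4.4 states that "Stages 2-4 form a randomised stepped wedge design" and that this allows questionnaire answers and returned samples to be compared between delivery modes. Stage 2 "is a larger transition of a random 25% of participants not included in Stage 1", Stage 3 "is a larger transition of a random 35% of participants not included in Stage 1", and Stage 4 "is the final transition of the remaining 40% participants".

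The paragraph after the stage definitions describes the allocation differently. Randomisation is to be stratified, with "households with under-represented characteristics, longest participation and fewest missed visits prioritised for randomisation in Stage 2 and 3", while everyone else goes to Stage 3 or 4. An earlier paragraph of the section lists who is to be retained first when the sample is cut: non-White ethnicity, higher deprivation, smaller households, giving blood, longest participation and fewest missed visits. Whether that list also defines the strata is not stated.

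During each of Stages 2, 3 and 4, swab and antibody positivity is then "compared between those randomised to transition to the new approach to delivery and returning swab tests and those randomised to still receive study worker visits". The listed adjustments are sex, age, ethnicity, region, deprivation and household size. With analyses of response rates by these factors, the result is used to judge whether later adjustment for response is needed. Section 11.1 says there is no formal statistical analysis plan, so this text is the plan for the comparison.

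**The concern.** If Stages 2 and 3 were simple random samples, those already moved and those still visited at home would be alike apart from delivery mode and chance. Under the stratified rule they are not: stage depends on how long a household has taken part and how many visits it has missed. Neither variable is in the adjustment list, nor is the stratum itself. If long-standing, reliable participants differ in positivity from the rest after the six listed adjustments, that difference would appear as an effect of mode, or would mask a real one.

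What is at stake is the judgement on whether the positivity series needs further adjustment after the change of delivery. The factors that Section 11.2 names for the primary model include no term for delivery mode, so that judgement rests largely on this comparison and the accompanying response-rate analyses.

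**Working it through.** **1. Stage shares.** 100% − 25% − 35% = 40%, which matches the stated Stage 4 share. All three shares refer to the same pool.

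**2. Balance between modes.** Let P be the proportion of participants in priority households. The protocol does not give it. Take the text that priority households are "prioritised for randomisation in Stage 2 and 3, and other participants randomised across Stages 3 and 4" strictly: Stage 2 holds only priority households and Stage 4 only others. P must then lie between 25% and 60%.

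- Stage 2 period (Stage 2 on the new mode, Stages 3 and 4 on home visits): gap in priority share = 1 − (P − 0.25)/0.75.
- Stage 3 period (Stages 2 and 3 on the new mode, Stage 4 on home visits): gap = P/0.60 − 0.

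| P | Stage 2 period: new mode v home visits | Gap | Stage 3 period: new mode v home visits | Gap | Priority stratum in Stage 2 | Others in Stage 3 |
|---|---|---|---|---|---|---|
| 25% | 100% v 0% | 100 | 41.7% v 0% | 42 | 100% | 47% |
| 40% | 100% v 20% | 80 | 66.7% v 0% | 67 | 62.5% | 33% |
| 60% | 100% v 46.7% | 53 | 100% v 0% | 100 | 42% | 0% |

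Simple random samples would have an expected gap of 0. A softer reading, in which priority only raises the chance of an early stage, narrows the gap but does not close it. With P = 40% and half of the priority group in Stage 2, the Stage 2 period shares are 0.20/0.25 = 80% against 0.20/0.75 = 27%.

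**3. What the adjustment covers.** Ethnicity, deprivation and household size are in the model. Length of participation, missed visits and stratum are not. Nor is blood-giving, if the retention list carries over.

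**4. Illustration of size.** Assumptions: positivity 3% (Section 11.3 speaks of rates above 3%); 100,000 visits a week, so 400,000 per four-week stage; return of 81% × 90% = 72.9% (Section 9.4.4); other households' positivity is r times that of priority households through factors not adjusted for. The value of r is assumed.

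- Priority positivity = 0.03/(P + (1 − P)r). At P = 40% and r = 1.10 this is 0.03/1.06 = 2.83%, against 3.11% in others, a difference of 0.283 points.
- Spurious mode difference = gap × difference: 0.80 × 0.283 = 0.23 points (Stage 2 period) and 0.667 × 0.283 = 0.19 points (Stage 3 period), with the new mode looking lower. If r were below 1 the sign would reverse.
- SE = √[0.03 × 0.97 × (1/n₁ + 1/n₀)]. Stage 2 period: n₁ = 0.729 × 100,000 = 72,900 and n₀ = 300,000, giving 0.070 points. Stage 3 period: n₁ = 0.729 × 240,000 = 174,960 and n₀ = 160,000, giving 0.059 points.
- Worst-case clustering: Section 11.3's conservative assumption that household members share one status, with 2.16 people per household (Table 1), multiplies the SE by √2.16 = 1.47, giving 0.104 and 0.087 points.

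| r (assumed), P = 40% | Stage 2 period: bias; bias/SE simple, clustered | Stage 3 period: bias; bias/SE simple, clustered |
|---|---|---|
| 1.05 | 0.12; 1.7, 1.1 | 0.10; 1.6, 1.1 |
| 1.10 | 0.23; 3.2, 2.2 | 0.19; 3.2, 2.2 |
| 1.20 | 0.43; 6.1, 4.1 | 0.36; 6.1, 4.1 |

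These ratios are upper-end for a given r. The 81% opt-in builds up mainly over six weeks and up to one home visit may follow the invitation, so fewer posted swabs would arrive within a stage than assumed.

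**The case against.** The strongest reply is that the protocol says openly that randomisation is stratified. Allocation within a stratum is still random, and nothing states that the analysis will pool strata. That stands: a valid contrast can be recovered, and the defect lies in the stated analysis. But the adjustment list is explicit, it omits the stratum and two of the variables that form it, and no within-stratum comparison is described.

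Four stronger readings are tempting and are not supported:

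- *That the under-represented characteristics confound the comparison as well.* The three demographic ones named in Section 9.4.4 (ethnicity, deprivation, household size) are all adjusted for. The open route is adherence, and possibly blood-giving.
- *That priority households cannot be in Stage 4.* The text says they are prioritised for Stages 2 and 3; only the placing of other participants in Stages 3 and 4 is explicit.
- *That Stage 4 has no randomised control at all.* The stage dates are start dates for invitations. Home visits continue for those not yet invited, with up to one visit afterwards, and visits are foreseen in June and July 2022. Stage 4 households can therefore supply home-visit swabs early in that stage.
- *That restricting the new-mode group to those returning swabs is simply an error.* The stated purpose includes judging the need for response adjustment, so looking at responders partly fits it. It is still selection after randomisation in one group: on the protocol's figures 1 − 0.729 = 27% of those allocated would not contribute. Part of the planned Stage 4 group may also be dropped, depending on opt-in.

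**Conclusion.** The point holds as a fault in the stated analysis. The description of random 25% and 35% samples does not agree with the stratified allocation in the same section, and a comparison carried out as written would be open to confounding by length of participation and missed visits.

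The imbalance follows from the protocol's own rule: 53 to 100 points of priority share in the Stage 2 period and 42 to 100 in the Stage 3 period on the strict reading, less on a softer one. The bias in positivity is not known. It needs a positivity difference by adherence that survives the six adjustments, and the protocol gives none. With an assumed 10% relative difference and P = 40%, it would be about 0.2 points, or about 2 standard errors under worst-case household clustering; with 5% it would be about 1.

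A reader might infer that the primary prevalence estimate is itself biased. The protocol does not support that: the mode comparison is not a listed objective, and it bears on prevalence only through the later decision on response adjustment.

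**What to change.** In Section 9.4.4:

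1. Reconcile the random 25% and 35% wording with the stratified allocation, define the strata (including whether blood-giving counts), and state how each stratum is split across stages.
2. Compare modes within randomisation stratum where both arms exist: priority households, Stage 2 against Stage 3; others, Stage 3 against Stage 4. At the least, add stratum, time in study, missed visits and blood-giving to the model, with calendar time and household clustering.
3. Beside the comparison in those returning swabs, add an analysis by assigned stage with response weights.
4. Limit the Stage 4 period contrast to the time when Stage 4 households still have home visits, and label any later contrast non-randomised.

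This changes analysis wording and uses data the study already holds. The price is somewhat fewer participants per contrast. A contrast is also lost if a stratum is not actually split: on the strict reading, at P = 25% no priority household is left in Stage 3, and at P = 60% no other household is in Stage 3. That is why the split has to be stated.
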